## 8. Discontinuation Criteria

### 8.1. Discontinuation of Study Treatment

In considering discontinuation of the study treatment, the Investigator should give particular consideration of the following:

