### ECG Abnormalities

If a clinically significant finding is identified (including but not limited to changes from baseline in QTcF after enrolment), the Investigator or qualified designee will determine if the participant can continue in the study and if any change in participant management is needed. This review of the ECG printed at the time of collection must be documented. Any new clinically relevant finding should be reported as an AE.

When the following ECG change conditions are met, study treatment **MUST** be discontinued, the DCC and study PI informed, and further steps discussed:

- Absolute QTcF >500 ms or >60 ms increase from baseline as confirmed with 3 consecutive ECGs taken in a 30-minute period with at least 5 minutes between each ECG. The mean of the 3 ECGs will be used for decision making.

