### Other Laboratory Parameters

Study treatment **MUST** be discontinued if the following laboratory parameters criteria are met:

- Absolute neutrophil count less than or equal to  $1.0 \times 10^9/L$  on 2 consecutive repeat tests within 48 to 72 hours.

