### 9.4.3. Adverse Events of Special Interest

Some AEs, regardless of their severity or outcome, will be expedited due to the relevance for subject safety or study treatment safety profile. These events should be reported to the DCC within 24 hours, as indicated in [Appendix 4](#). The AESIs for alvelestat (MPH966) are:

- Liver function abnormalities defined as:
  - a) Any occurrence of (i) ALT or AST elevations  $>5 \times \text{ULN}$  or (ii) ALT or AST  $>3 \times \text{ULN}$  and total bilirubin  $>2 \times \text{ULN}$  or INR  $>1.5$  or the appearance of worsening fatigue, nausea, vomiting, RUQ pain/tenderness, fever, rash, or eosinophilia.
  - b) Any occurrence of  $<5 \times \text{ULN}$  or ALT or AST  $<3 \times \text{ULN}$  and total bilirubin  $<2 \times \text{ULN}$  where the tests have been repeated within 48 to 72 hours and the elevation confirmed on at least 2 separate occasions.

For participant safety and to ensure that the hepatotoxic potential of the study treatment to be determined, a standardized procedure for identification, monitoring, and evaluation of liver events must be followed as outlined in [Section 9.3.3](#) and [Section 8.1](#).

- ECG/Cardiac Events

If a study subject experiences any of the following cardiovascular events, the event should be reported immediately as an AESI and the study treatment discontinued:

- a) Absolute QTcF >500 ms or >60 ms increase from baseline.
- b) Any clinically significant cardiac abnormality on ECG.

- Infection

Any new infection that requires the use of systemic antimicrobial treatment (antibiotics, anti-viral, anti-fungal, or anti-mycobacterial) should be investigated with clinically relevant diagnostic tests.

Acute exacerbations of COPD are considered AESI.

- Neutropenia

- a) Absolute neutrophil count less than or equal to  $1.0 \times 10^9/L$  on 2 consecutive repeat tests within 48 to 72 hours.

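### Protocol Section 9.4.3 tells sites to stop study drug on an unconfirmed QTcF reading, while Section 8.1 requires triplicate confirmation; its stop for other ECG findings is ambiguous against Section 8.1

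*Protocol*

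**What the plan says.** **Section 9.4.3, ECG/Cardiac Events.** If a participant has any listed event, "the event should be reported immediately as an AESI and the study treatment discontinued". Item (a) is a QTcF above 500 ms or more than 60 ms over baseline. Item (b) is "Any clinically significant cardiac abnormality on ECG". The bullet has no repeat tracing and no pointer to Section 8.1.

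**Section 8.1, ECG Abnormalities.** The mandatory stop uses the same two QTcF limits, but "as confirmed with 3 consecutive ECGs taken in a 30-minute period with at least 5 minutes between each ECG", and adds: "The mean of the 3 ECGs will be used for decision making". For a clinically significant finding in general, "the Investigator or qualified designee will determine if the participant can continue in the study and if any change in participant management is needed".

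**Section 9.3, Electrocardiograms, and SAP Section 4.5.4.** Scheduled ECGs are single tracings. When a change meets the drug-stopping criteria, three tracings are needed to confirm it and to decide on stopping. The protocol text sends the reader to Section 8.1 for the QTc withdrawal criteria.

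**The concern.** Two sections of one protocol give a stopping rule for the same QTcF limits, and only one of them asks for confirmation. Site staff handling an ECG event of special interest would naturally turn to Section 9.4.3, and nothing in that bullet sends them on to the triplicate rule. A participant whose single reading crosses a limit, but whose triplicate mean does not, could lose study drug at one site and keep it at another.

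Item (b) raises a second, softer question. It attaches a stop to a class of finding for which Section 8.1 describes a judgement by the investigator.

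What is at stake is uniform handling of drug across sites for a risk the protocol chose to monitor closely. Section 5.8 cites the QTc changes in dogs as the reason for the ECG monitoring and stopping criteria.

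**Working it through.** There is no sample size, power or error rate to recompute. The check is a comparison of the texts.

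**Item (a), QTcF**

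| Place | Limits | Confirmation before drug is stopped |
|---|---|---|
| Protocol 9.4.3(a) | >500 ms, or >60 ms rise | None stated |
| Protocol 8.1 | Same | Three consecutive ECGs within 30 minutes, at least 5 minutes apart; mean used |
| Protocol 9.3, Electrocardiograms | Refers to 8.1 | Triplicate required |
| SAP 4.5.4 | Refers to the Protocol | Triplicate required |

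Three places require the triplicate and one omits it. The SAP entry repeats the protocol's ECG text, so it adds little independent weight. Because scheduled tracings are single, the literal result of 9.4.3(a) is a stop on one reading. The rules part company in one case: the first reading is over a limit and the triplicate mean is not. Section 9.4.3 then stops drug, and Section 8.1 does not require it.

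**Item (b), other ECG findings**

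1. Section 9.4.3(b) stops drug for any clinically significant ECG abnormality.
2. The mandatory list in Section 8.1 has no such entry. Its ECG paragraph leaves the finding to the investigator or a designee.
3. That paragraph speaks of continuing in the study. Section 8.1, under Other, separates a participant's decision to stop drug from leaving the study. Reading the paragraph as covering drug is therefore an inference, supported by the Section 8.1 heading and its lead-in: "In considering discontinuation of the study treatment, the Investigator should give particular consideration of the following".
4. Section 8.1, under Other, also requires a stop when the site investigator sees a significant safety issue.
5. What remains open is a finding judged clinically significant but not a significant safety issue. Section 9.4.3 says stop; Section 8.1, on the reading in step 3, leaves it to judgement.

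**The other bullets in Section 9.4.3**

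- Liver: no stop of its own. It says that "a standardized procedure for identification, monitoring, and evaluation of liver events must be followed as outlined in" Sections 9.3.3 and 8.1.
- Neutropenia: no stop of its own, and its definition carries the Section 8.1 condition, "on 2 consecutive repeat tests within 48 to 72 hours".
- Infection: no stop.
- ECG/cardiac: its own stop, with no confirmation and no cross-reference.

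So 1 of the 4 bullets carries its own stop instruction.

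**How often it could arise.** The Schedule of Activities gives post-dose ECG occasions before the Week 12 visit at Visit 3 (post-dose) and Visits 4, 5, 6, 8 and 9: 1 + 5 = 6 per participant. The documents give no rate of unconfirmed QTcF readings or of clinically significant non-QTc findings, so no expected count can be derived.

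**The case against.** On (a), the protocol already answers the question. Its ECG text requires a triplicate for stopping decisions, makes no exception for Section 9.4.3 and points to Section 8.1. The triplicate fits in 30 minutes and doses are 12 hours apart, so confirmation can normally be had before the next dose. This stands as evidence of intent: the omission is a slip in wording, and a careful site would probably confirm first. It does not make the Section 9.4.3 instruction correct as written.

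On (b), a reader might infer that the two sections flatly contradict each other. The documents do not support that. The mandatory list in Section 8.1 is never said to be complete, the investigator's judgement there can include stopping drug, and a site that stops satisfies both texts. A strict rule also fits the caution in Section 5.8. This objection largely stands, so (b) is an ambiguity for the sponsor to settle.

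A reader might also infer that the ECG bullet is the only one whose definition is looser than Section 8.1. It is not. The liver definition counts any occurrence of ALT or AST above 5 times the upper limit of normal, where Section 8.1 requires two consecutive tests. A reporting definition broader than a stopping rule is reasonable. What is peculiar to the ECG bullet is the stop attached to it.

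**Conclusion.** The point holds as a minor inconsistency. For QTcF, the stop in Section 9.4.3 conflicts with Section 8.1 and with the ECG text in the protocol and SAP, and should be corrected. For other clinically significant ECG findings, the sections leave the intended rule unclear without strictly contradicting each other.

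It is tempting to go further and say that the primary safety endpoint is affected, because QTc/cardiac events are among the events of special interest. The documents do not support that: the endpoint counts events, and the discrepancy concerns what is done with drug afterwards. There is no effect on power, bias, any inferential test or the count of these events. The effect is confined to whether drug is stopped uniformly across sites. Its frequency cannot be estimated from the documents.

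The conclusion on (a) rests on the literal wording of Section 9.4.3. The conclusion on (b) also rests on reading the Section 8.1 ECG paragraph as covering study drug.

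**What to change.** Leave the AESI definitions in items (a) and (b), and immediate reporting, exactly as they are, including for a QTcF reading not yet confirmed. Writing the triplicate into the definition of (a) would narrow what is reported under a primary safety endpoint, and should be avoided.

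Change only the stop instruction for (a), for example: *Report the event at once as an AESI. For item (a), discontinue study treatment if triplicate ECGs confirm it, per Section 8.1.*

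For (b), keep the stop as written until the sponsor confirms the intended rule, so that the edit does not loosen protection by default. Then state the same rule in both sections: either add the item to the mandatory list in Section 8.1, or refer (b) to investigator determination under Section 8.1.

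The cost is a wording change in one bullet and, if the stricter rule is chosen, one added line in Section 8.1. As a protocol amendment it needs IRB approval under Appendix 3. No new assessment is needed, because the triplicate is already required, and the SAP does not change.

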#### 9.4.4. Regulatory Reporting Requirements for SAE

- Prompt notification by the Investigator to the DCC of an SAE is essential so that legal obligations and ethical responsibilities towards the safety of participants and the safety of a study treatment under clinical investigation are met.
- The DCC, the NCATS Medical Monitor, as well as Mereo have a legal responsibility to notify both the local regulatory authority and other regulatory agencies about the safety of a study treatment under clinical investigation.
- Investigator safety reports must be prepared for suspected unexpected serious adverse reactions (SUSARs) according to local regulatory requirements and will be forwarded to Investigators as necessary.
- An Investigator who receives an Investigator safety report describing an SAE or other specific safety information (e.g. summary or listing of SAEs) will file it along with the Investigator's Brochure and will notify the IRB/IEC, if appropriate according to local requirements.

#### 9.4.5. Pregnancy

- Details of all pregnancies in female participants and female partners of male participants will be collected after the start of study treatment and until 5 half-lives (4 days) after the last dose.
- If a pregnancy is reported, the Investigator should inform the DCC within 24 hours of learning of the pregnancy and should follow the procedures outlined in [Appendix 5](#).
- Abnormal pregnancy outcomes (e.g. spontaneous abortion, fetal death, stillbirth, congenital anomalies, ectopic pregnancy) are considered SAEs.

## Partner Pregnancies

Pregnancy outcomes must be collected for the female partners of the subjects who took study treatment in this study. Pregnancy itself is not regarded as an AE unless there is suspicion that the study treatment may have interfered with the effectiveness of a contraceptive medication. If a pregnancy is reported for a subject's partner, study treatment will be immediately discontinued. The outcome of all pregnancies (spontaneous miscarriage, elective termination, normal birth, or congenital abnormality) must be followed and documented. A follow-up report should be sent with any new information regarding the pregnancy and the outcome of the birth.

### 9.5. Treatment of Overdose

For this study, any dose of alvelestat (MPH966) greater than 120 mg bid within a 24-hour time period will be considered an overdose.

There is no specific treatment for an overdose. Any treatment should be supportive as indicated by the subject's condition.

In the event of an overdose, the Investigator/treating physician should:

1. Contact the DCC and study PI immediately.
2. Closely monitor the participant for AE/SAE and laboratory abnormalities until alvelestat (MPH966) can no longer be detected systemically (at least 3 days).
3. Obtain a plasma sample for PK analysis within 3 days from the date of the last dose of study treatment if requested by the DCC and/or study PI (determined on a case-by-case basis).
4. Document the quantity of the excess dose as well as the duration of the overdosing in the CRF.

Decisions regarding dose interruptions or modifications will be made by the Investigator in consultation with the Study PI as necessary based on the clinical evaluation of the participant.

### 9.6. Pharmacokinetics

Sparse PK sampling will be performed before and after study treatment dosing as detailed in the SoA and MOP.

- Blood samples of approximately 3 mL will be collected for measurement of blood concentrations of alvelestat (MPH966) as specified in the SoA. Instructions for the collection and handling of biological samples will be provided by the DCC. The actual date and time (24-hour clock time) of each sample will be recorded.

### 9.7. Pharmacodynamics

Pharmacodynamic markers form the primary, and some secondary and exploratory efficacy endpoints in this study and are covered in [Section 9.2.1](#).

## 10. Statistical Considerations

### 10.1. Sample Size Determination

Over the course of the study, approximately 60 participants will be randomized in a 1:1 ratio to receive one of the following: 120mg alvelestat (MPH966) BID or placebo. Randomization will be stratified by study site and by AAT genotype/phenotype.

The study will be powered for within-individual change in plasma desmosine/isodesmosine as the primary endpoint at Week 12 compared to baseline. A sample size of 30 participants in the MPH966 treatment group will give us >90% power to detect a 15% mean decrease of plasma DES from baseline to 12 weeks follow-up in patients treated with MPH966 (within subject change) using a two-sided paired t-test at  $\alpha=0.05$ . This 15% mean decrease has been observed in trials of standard dose augmentation versus placebo. A recent study of double dose versus single dose augmentation revealed a within subject decrease in plasma DES from 0.42 +/-0.03 ng/ml to 0.38 +/- 0.03 ng/ml. We will have 80% power to detect a comparable difference in DES in those who have alvelestat added to augmentation.

For comparing the mean change in DES between the two groups (placebo vs. MPH966), and assuming that there is no placebo effect over 12 weeks, a two-sided two sample t-test at  $\alpha=0.05$  with a sample size of 60 (30 per group) reveals that we will have 82% power to detect a 15% difference in mean change in plasma DES.

Other secondary endpoints (BAL and sputum DES, other serum, sputum and BAL inflammatory markers, patient-reported outcomes, and pulmonary function) will be examined within and between group with paired t-tests or mixed effect modeling as appropriate.

We will also examine the association between DES at baseline and response to treatment as measured by change in pulmonary function (FEV1) over 12 weeks within the MPH966 treatment group. With a sample size of 30, we will have 80% power to detect a 0.12 regression correlation coefficient of DES at baseline in predicting the change of FEV1 over 12 weeks when the standard deviation of DES is 0.10 and  $\alpha=0.05$ .

By including a 10% attrition rate over 12 weeks, the required sample size is inflated to 66 (33 per group) to achieve the estimated powers. If we observe attrition rate less than we expected, we will have more statistical power to detect the expected differences. As one interim analysis will be conducted only for safety concerns (see Data Safety and Monitoring Plan), no adjustments to the Type I error is considered for estimating statistical powers.

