#### Type of Participant and Disease Characteristics

1. Capable of giving signed informed consent as described in [Appendix 3](#), which includes compliance with the requirements and restrictions listed in the informed consent form and in this protocol
2. Age  $\geq 18$  and  $\leq 80$  years
3. Patients with a confirmed diagnosis of AATD: Pi\*ZZ, Pi\*SZ, Pi\*null, or another rare phenotype/genotype known to be associated with either low (serum AAT level  $< 11 \mu\text{M}$  or  $< 57.2 \text{ mg/dL}$ ) or functionally impaired AAT including "F" or "I" mutations.
4. FEV1  $\geq 25\%$  predicted
5. Patients will be eligible if they are either a) are not currently receiving augmentation treatment and have not received augmentation in the 12 weeks prior to screening or b) have received weekly infusions of augmentation at 60 mg/kg for at least 12 weeks prior to screening and intend to continue augmentation through the study period.
6. Male or female sex
  - a. Male participants must agree to use a highly effective contraception as detailed in [Appendix 5](#) during the treatment period and for at least 4 days after the last dose of study treatment and refrain from donating sperm during this period
  - b. Female participants are eligible to participate if not pregnant; not breastfeeding; and at least one of the following conditions is met:
    - i. Not a woman of childbearing potential as defined in [Appendix 5](#)
    - OR
    - ii. A woman of childbearing potential who agrees to follow the contraceptive guidance in [Appendix 5](#). During the treatment phase and for at least 4 days after the last dose of study medication.

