### 7.2. Method of Treatment Assignment

All participants will be centrally randomized 1:1 to the 120 mg and placebo arms using an interactive web response system (IWRS). A unique number will be assigned to each participant and will be linked to randomization numbers using a randomization list produced by the DCC. These randomization numbers will be linked to the 2 treatment regimens, and the randomization scheme will be stratified according to genotype (Pi\*ZZ, Pi\*SZ, Pi\*(Null) (Null)) and clinical center.

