**Appendix 7: Summary of Versions and Changes**

Protocol	Version	Date	Summary of Change
Original	1.0	September 5, 2018	Not Applicable
Revision 1	1.1	October 26, 2018	Eligibility and safety modifications per FDA request (see also Table of Protocol changes October 26, 2018)
Revision 2	1.2	July 31, 2019	Eligibility and safety modifications (see also Table of Protocol changes July 31, 2019)
Revision 3	1.3	February 18, 2020	Eligibility modifications to include participants on augmentation therapy and safety updates (also see Table of Protocol changes February 18, 2020)
Revision 4	1.4	February 10, 2021	Eligibility modifications to include participants with other rare genotypes/phenotypes at increased risk for emphysema. (also see Table of Protocol changes February 16, 2021)

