# 3.5.3 Sample Size

Over the course of the study, target enrolment is 66 with the goal of 60 completers. Participants will be randomized in a 1:1 ratio to receive one of the following: 120mg Alvelestat (MPH966) BID or placebo. Randomization will be stratified by AAT genotype/phenotype.

The study will be powered for within-individual change in plasma desmosine/isodesmosine (DES) as the primary endpoint at Week 12 compared to baseline. A sample size of 30 participants in the MPH966 treatment group will give us >90% power to detect a 15% mean decrease of plasma DES from baseline to 12 weeks follow-up in patients treated with MPH966 (within subject change) using a two-sided paired t-test at  $\alpha$ =0.05. The calculation is based on an assumed correlation value of 0.5, baseline mean DES value of 0.466 and standard deviation of 0.09. This 15% mean decrease has been observed in trials of standard dose augmentation versus placebo (Ma S, 2013). A recent study of double dose versus single dose augmentation revealed a within subject decrease in plasma DES from 0.42 +/-0.03 ng/ml to 0.38 +/- 0.03 ng/ml (Campos MA, 2019). We will have >99% power to detect a comparable difference in DES in those who have Alvelestat added to augmentation if we assume their observed SD=0.03 and 85% power if we double their assumed SD, i.e., SD=0.06. Power will not be enough (~50%) to detect this difference if we use our original SD value of 0.9.

For comparing the mean change in DES between the two groups (placebo vs. MPH966), and assuming that there is no placebo effect over 12 weeks, a two-sided two sample t-test at  $\alpha$ =0.05 with a sample size of 60 (30 per group) reveals that we will have 82% power to detect a 15% difference in mean change in plasma DES.

By including a 10% attrition rate over 12 weeks, the required sample size is inflated to 66 (33 per group) to achieve the estimated powers. If we observe attrition rate less than we expected, we will have more statistical power to detect the expected differences. As one interim analysis will be conducted only for safety concerns (see Data Safety and Monitoring Plan), no adjustments to the Type I error are considered for estimating statistical powers.

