All participants will be centrally randomized 1:1 to the 120 mg and placebo arms using an interactive web response system (IWRS). A unique number will be assigned to each participant and will be linked to randomization numbers using a randomization list produced by the DCC. These randomization numbers will be linked to the 2 treatment regimens, and the randomization scheme will be stratified according to genotype (Pi\*ZZ, Pi\*SZ, Pi\*(Null) (Null))

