# 6.3 Covariates and Subgroups

Prespecified covariates have been provided in the above efficacy analyses. Covariates to be included in the primary and secondary efficacy analyses on change in the biomarkers are baseline values, age and smoking history. Although we have stratified randomization by genotype, we will not include genotype as a covariate in the main analyses. Depending on available data, we may be able to compare outcomes between genotypes, but this will be exploratory in nature.

Due to the change in protocol to drop augmentation therapy from the exclusion criterion, subgroup analyses between those enrolled with and without augmentation will be performed as secondary analyses.

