# 6.5 Multi-center Studies

This study was a multi-center study. Data will be analyzed by combining data from all study centers. No investigation of center effects is planned.

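### Protocol and SAP disagree on whether centre was a randomisation stratum, the named genotype strata leave rare genotypes unplaced, and the SAP 8.2 placebo comparison omits genotype, a stratum in both documents

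*Protocol*

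**What the plan says.** **Stratification factors.** Protocol 10.1: "Randomization will be stratified by study site and by AAT genotype/phenotype". Protocol 7.2 lists three genotype levels and then adds centre: "Null) (Null)) and clinical center". SAP 3.5.3 says "Randomization will be stratified by AAT genotype/phenotype". Its allocation paragraph says "the randomization scheme will be stratified according to genotype" and gives the same three levels, with no mention of centre. SAP 6.3 also refers to genotype only. SAP section 10, which lists departures from the protocol analysis, is silent on this.

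**Levels.** Both documents name Pi*ZZ, Pi*SZ and Pi*(Null)(Null). Inclusion criterion 3 is wider and also admits "or another rare phenotype/genotype known to be associated with either low" or functionally impaired AAT. Protocol Appendix 7 describes version 1.4 as "Eligibility modifications to include participants with other rare genotypes/phenotypes at increased risk for emphysema". Neither document describes a further level.

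**Analysis.** The SAP 8.2 model contains baseline, treatment, visit, their interaction, FEV1, age and smoking. SAP 6.3 states: "Although we have stratified randomization by genotype, we will not include genotype as a covariate in the main analyses". SAP 6.5 combines all centres and adds: "No investigation of center effects is planned".

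**The concern.** There are two problems.

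- **Description of allocation.** Patients were allocated under one scheme. The SAP was written after allocation was well under way, since its section 11 reports the interim safety analysis in the past tense. Yet the two documents describe the scheme differently, and neither says how a patient outside ZZ, SZ or Null/Null was placed. A statistician cannot tell from them which terms would make the analysis follow the randomisation.
- **Analysis.** Stratifying balances a factor between arms, so the treatment difference varies less from trial to trial. A model without that factor leaves its variance in the residual and takes no credit for the balance. If the factor predicts outcome, the standard error is too large, the test rejects too rarely under the null, and power is lost.

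At stake is the precision of the comparisons with placebo, including plasma desmosine/isodesmosine (DES) against placebo. These are secondary, but they are the trial's randomised efficacy evidence.

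**Working it through.** **1. The texts side by side.**

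| Item | Protocol | SAP |
|---|---|---|
| Factors | Genotype and centre (7.2, 10.1) | Genotype (3.5.3, 6.3) |
| Named levels | ZZ, SZ, Null/Null (7.2) | Same three (3.5.3) |
| Eligible | Also other rare types, including F or I (6.1) | Same (3.5.1) |
| Between-arm model | Baseline, treatment, sputum strata (10.3.1) | Baseline, treatment by visit, FEV1, age, smoking (8.2) |

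Genotype is a stratum in both columns and a model term in neither. Centre is a stratum in one column and a model term in neither.

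**2. The plan's between-arm power.** SAP 3.5.3 gives 82% for 30 per arm, two-sided 0.05 and a 15% difference. For its paired calculation it gives a mean of 0.466, an SD of 0.09 and a correlation of 0.5. Taking these inputs:

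- difference = 0.15 × 0.466 = 0.0699
- SD of change = 0.09 × √(2 × (1 − 0.5)) = 0.09
- two-sample t power = 84.1%, against 82% stated

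An SD of change of about 0.0926 would give 82%. The between-arm SD is not stated separately, and nothing here depends on the gap. The stated 82% is the starting point below.

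**3. Effect of omitting a prognostic stratum.** Let R be the share of outcome variance explained by the omitted factor. The documents give no value, so 5% and 10% are assumptions. With near-perfect balance within strata and a normal approximation:

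- k = 1/√(1 − R) is the factor by which the unadjusted standard error is overstated
- true two-sided error = 2 × (1 − Φ(1.96k))
- 82% power means z = 0.915, so the standardised effect is 0.915 + 1.96 = 2.875
- power without the factor, under stratified allocation = Φ((2.875 − 1.96)k)
- power with the factor = Φ(2.875k − 1.96)

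| R | k | True error | Power without | Power with | Gain (points) |
|---|---|---|---|---|---|
| 5% | 1.026 | 4.4% | 82.6% | 83.9% | 1.3 |
| 10% | 1.054 | 3.9% | 83.3% | 85.8% | 2.5 |

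**4. Simulation.** Sixty patients were allocated 1:1 in blocks of 4 within three genotype strata. The mix was an assumed 80/15/5%, the SD of change 0.09 and the difference 0.0699, with 5,000 runs per cell. Each cell shows the result without / with strata terms.

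| R (assumed) | Type I error | Power |
|---|---|---|
| 0% | 5.0% / 4.9% | 84.6% / 84.1% |
| 10% | 4.0% / 4.8% | 84.7% / 87.1% |
| 20% | 3.3% / 4.7% | 86.1% / 91.1% |
| 30% | 2.4% / 5.0% | 86.5% / 93.7% |

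The 10% row agrees with step 3. In the 0% row, adjustment costs about half a point.

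**5. Less perfect balance.** If an assumed 12 centres are crossed with three genotypes in 60 patients, many blocks stay incomplete. With a centre effect explaining 5% or 10% of variance, the unadjusted error was about 4.6% and 4.2%. For that scheme, step 3 overstates the conservatism.

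**The case against.** The strongest reply has five parts.

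- **The omission is disclosed.** SAP 6.3 acknowledges the stratification, leaves genotype out and makes genotype comparisons exploratory. This stands, so the model point is a weakness and not a contradiction. No reason is given, however.
- **The SAP removed nothing.** A reader might infer that it dropped factors the protocol would have adjusted for. It did not: the ANCOVA in Protocol 10.3.1 contains neither genotype nor centre. What goes unrecorded is the different description of the randomisation.
- **The primary analysis is untouched.** It is fitted separately by arm (SAP 8.1), so a missing stratum cannot distort a between-arm contrast there. This stands and limits the point to secondary comparisons in a study the SAP calls signal-seeking.
- **The harm is conditional and small.** No passage shows that genotype or centre predicts percent change in DES beyond the covariates already in the model. The 82% also belongs to a two-sample t-test, not to the 8.2 model. Setting 82% against the adjusted 84-86% would suggest a gain of roughly 2 to 4 points, but that compares unlike quantities. Stratified allocation already raises the unadjusted power to 82.6-83.3%.
- **The wording gap may be clerical.** In the text available, the allocation sentence in SAP 3.5.3 ends without a full stop after the strata, so words may be missing there. But the earlier statement in 3.5.3 is complete and also omits centre. The system may equally have held a further level for other genotypes; neither document says so.

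**Conclusion.** The point holds in limited form. The documents conflict on centre, do not say where rare genotypes were placed, and specify a between-arm model without genotype, which is a stratum on either account.

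The consequence is mild conservatism in the secondary placebo comparisons. At an assumed 5-10% of variance explained and near-perfect balance, the error is about 4.4-3.9% and adjustment gains about 1.3-2.5 power points. The gain disappears, with a cost of at most about 1 point, if the factor is not prognostic. Balance spread thinly over many centres brings the error closer to 5%.

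A reader might infer that the mismatch produces false positives, or that allocation failed for rare genotypes. Neither follows. Omitting a stratification factor lowers the type I error or leaves it unchanged, and silence about a level does not show that it was absent from the system.

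**What to change.** 1. State in both documents the factors and levels the interactive web response system actually used, including the level that received rare genotypes. Correct whichever document is wrong, and record the difference in SAP section 10.
2. Add genotype to the SAP 8.2 model using those levels. Pool sparse levels by a rule set before unblinding, for example ZZ versus non-ZZ. That split is only an illustration, and the rule should follow from the levels used.
3. If centre was a stratum, add centre with small sites pooled by a rule set before unblinding. If the main model does not converge with it, report the centre-adjusted result as a sensitivity analysis.
4. Amend SAP 6.3 and 6.5 to match.

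The cost is some SAP wording and one or two model terms. Genotype is already tabulated (SAP 7.3), and data are already listed by site (SAP 6.1). The statistical price is one or a few degrees of freedom, a slight power loss if the factors are not prognostic, and some added convergence risk from a centre term in a model with an unstructured covariance and about 60 patients.
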